7.10.6 Concomitant Medications, Therapies, and Medical/Surgical Interventions

All non-protocol treatments, including medications and over-the-counter medications, therapies/interventions administered to subjects, and medical/surgical procedures performed on the subjects that started on or after the reference date, which is the date of the IDDD implantation surgery or the first dose of HGT-1410 (whichever is earlier) in either HGT-SAN-093 or SHP-610-201, to the data cut-off date, or 30 days after the date of last dose or 2 weeks after the date of device explant (whichever is later) if early termination, are regarded as concomitant. Any medications/surgical procedures which ended before the reference date will be excluded; however, a medication/surgical procedure that started before the reference date and ended on or after the reference date will be included. The Concomitant medications will be coded using the WHO DRUG Dictionary Enhanced December 2014 and presented in a listing.

7.10.7 Other Observations Related to Safety

7.10.7.1 IDDD Performance

The device failure/malfunction data will be presented in a listing only for the subjects in the safety population with an IDDD implant.

8. CHANGES IN THE CONDUCT OF THE STUDY OR PLANNED ANALYSES

8.1 Changes from the Analyses Planned in the Protocol

As this extension study will remain ongoing to allow for safety follow-up for patients with implanted devices (partial or full), despite the decision by Shire to terminate the development program, data for the treatment period of the study will be summarized in an abbreviated CSR. Not all data collected in this study will be analyzed. Summary statistics will only be presented for baseline characteristics, exposure of study drug, and adverse events. The data of selected efficacy endpoints will be presented in listings only. All outputs will be presented for safety population and no efficacy population will be defined. Information regarding the safety follow-up period will be analyzed after study completion and described in the final SAP.

The following data will not be analyzed: health status (ITQoL) and pharmacokinetic assessments.

However, SDTM data will be available for these endpoints.

10. APPENDICES

10.1 APPENDIX II: List of Statistical Outputs

A list of statistical outputs is provided in the TFL shells.

10.2 APPENDIX III: Definitions and Programming Conventions

10.2.1 Calculation of DQ Scores

BSID-III: Divide the Age-equivalent score for cognitive domain (expressed in months) by the Age at Testing (expressed in months). Multiply the result by 100 to obtain percentages. These values will be provided by an outside vendor, Prophase.

VABS-II: First calculate the average age equivalent score by averaging out the age-equivalent scores for the following sub-domains – receptive, expressive, written, personal, domestic, community, interpersonal relationships, play and leisure time, coping skills. Divide the average Age-equivalent score (expressed in months) by the Age at Testing (expressed in months). Multiply the result by 100 to obtain percentages. NOTE: The average age-equivalent score (hence DQ) will be calculated based on the available items if at least two items have non-missing value. These values will be provided by an outside vendor, Prophase.

STATISTICAL ANALYSIS PLAN

ADDENDUM

FOR SAFETY FOLLOW-UP PERIOD

Protocol Title: An Open-Label Extension of Study HGT-SAN-093
Evaluating the Safety and Efficacy of HGT-1410
(Recombinant Human Heparan N Sulfatase) Administration
via an Intrathecal Drug Delivery Device in Pediatric Patients
with Mucopolysaccharidosis Type IIIA Disease

Protocol Number: SHP-610-201

Protocol Date: 25 January 2017 (Amendment 2)

Investigational Product: Recombinant human heparan N-sulfatase (rhHNS, HGT-1410)
SOPH-A-PORT® Mini S, Implantable Access Port, Spinal,
Mini Unattached, with Guidewire

SAP Author(s): [REDACTED]

Release Date: 21 Jun 2019

Study Sponsor: Shire
[name]
[name]

Shire Medical Monitor: [REDACTED], DO

Confidentiality Statement

This document is the proprietary and confidential property of
Shire, Inc.

TABLE OF CONTENTS

| | |
|--|---|
| 1. ABBREVIATIONS AND DEFINITION OF TERMS..... | 3 |
| 2. RATIONALE FOR THE ADDENDUM..... | 4 |
| 3. GENERAL DESCRIPTION..... | 5 |
| 4. SAFETY VARIABLES..... | 6 |
| 4.1 Schedule of Safety Evaluations | 6 |
| 4.2 Safety Endpoints | 6 |
| 5. STATISTICAL ANALYSIS | 7 |
| 5.1 General Methodology | 7 |
| 5.2 Analysis Populations..... | 7 |
| 6. DATA DISPLAYS | 8 |
| 6.1 Subject Disposition | 8 |
| 6.2 Protocol Deviations..... | 8 |
| 6.3 Demographics and Other Characteristics..... | 8 |
| 6.4 Extent of Exposure..... | 8 |
| 6.5 Safety Analysis | 9 |

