2. INTRODUCTION

2.1 Purpose of the Statistical Analysis Plan

This statistical analysis plan (SAP) provides a technical and detailed elaboration of the planned interim analyses for protocol SHP-610-201 amendment 2, a Phase IIb, open-label extension of study HGT-SAN-093 evaluating the safety and efficacy of HGT-1410 (Recombinant Human Heparan N Sulfatase) administration via an intrathecal drug delivery device in pediatric patients with mucopolysaccharidosis type IIIA disease. Shire made a decision in August 2016 to terminate the Sanfilippo Syndrome Type A development program, including this extension study, due to the failure to meet the prespecified efficacy criteria in the pivotal Phase 2 study, HGT-SAN-093, and the resulting inability for the study to yield clinical proof-of-concept. After notification of early study termination, several investigators informed Shire that the IDDDs would remain implanted since in their opinion removal of devices would result in an increased risk to the patients. Therefore, this extension study (SHP-610-201) remains ongoing and has been extended to allow for safety follow-up of patients with partial or full devices still implanted after completion of the treatment period of the study. The statistical analyses and summary tabulations described in this interim SAP will provide the basis for the results sections of the abbreviated clinical study report (aCSR). An aCSR will be written to describe the results of the treatment period of the study, as the study is not intended to contribute to the evaluation of product effectiveness or to provide definitive information on clinical pharmacology. Full safety information will be reported.

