5.2 Secondary Endpoints

The secondary endpoints of this study are:

- The change from Baseline in BSID-III or KABC-II age-equivalent, DQ, and developmental delay scores
- The change from Baseline in adaptive behavioral function domains, assessed by VABS II, using raw scores, age-equivalent scores, and DQ scores
- The change from Baseline in total cortical grey matter volume, as assessed by MRI

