7. STATISTICAL ANALYSIS

7.1 General Methodology

Statistical analysis will generally be performed by the Biometrics Department of Shire using SAS statistical software (SAS Institute, Cary, NC, USA). Analysis of any PK and health economics and outcomes data will be performed by the Shire Clinical Pharmacology and Pharmacokinetics group and the Health Economics and Outcomes Research groups, respectively. The analysis methods for all other study data (demographic and baseline characteristics, efficacy variables, and safety variables) will be detailed in this SAP.

Summary statistics for continuous variables will include the n, mean, standard deviation, median, minimum, and maximum. Categorical variables will be summarized in a contingency table by the frequency and percentage of patients in each category.

Unless otherwise indicated, all summary statistics will be presented by treatment groups (either Q2W or Q4W) to which the patients were randomly assigned (for patients who were initially assigned to Q2W or Q4W group in Study HGT-SAN-093 or patients who were assigned to no-treatment in HGT-SAN-093 and were randomly assigned to Q2W or Q4W in Study SHP-601-201).

No summary statistics and hypothesis testing will be presented for efficacy data. Instead, subject listings will be presented for the selected efficacy endpoints.

Data from Study HGT-SAN-093 will be combined with that of Study SHP-610-201 for analysis, for subjects who enrolled in SHP-610-201. The data included for treated patients in HGT-SAN-093 starts from the baseline of Study HGT-SAN-093 and for patients who received no treatment in HGT-SAN-093 from the baseline of Study SHP-610-201. Baseline is the assessment obtained prior to the first dose of HGT-1410.

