7.8.2.2 Vineland Adaptive Behavior Scales, Second Edition (VABS-II)

The VABS-II data including age equivalent scores, DQ, raw scores, and standard scores for each domain will be presented in a listing only.

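### Does allowing the VABS-II DQ from any two of nine sub-domains, with no common set across visits, call for a change to the plan?

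*SAP*

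**What the plan says.** Section 10.2.1 of the interim SAP builds the VABS-II DQ by "averaging out the age-equivalent scores for the following sub-domains": "receptive, expressive, written, personal, domestic, community, interpersonal relationships, play and leisure time, coping skills". That is nine components. The average is divided by age at testing in months and multiplied by 100. The note on missing data says the average, and hence the DQ, "will be calculated based on the available items if at least two items have non-missing value". An outside vendor supplies the values. The SAP that precedes the interim SAP has the same wording in its own section 10.2.1.

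The secondary endpoint in section 5.2 is "The change from Baseline in adaptive behavioral function domains, assessed by VABS II, using raw scores, age-equivalent scores, and DQ scores".

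On reporting, section 7.1 rules out summary statistics and hypothesis tests for efficacy data, and says that "subject listings will be presented for the selected efficacy endpoints". Section 7.8.2.2 applies this to the instrument: "The VABS-II data including age equivalent scores, DQ, raw scores, and standard scores for each domain will be presented in a listing only". Section 10.1 leaves the layout elsewhere: "A list of statistical outputs is provided in the TFL shells". Section 2.1 says that "the study is not intended to contribute to the evaluation of product effectiveness".

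**The concern.** Three features together look like a fault.

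- **A low minimum.** A quantity defined on nine components may be computed from any two of them (22%).
- **No common set.** No section requires the sub-domains scored at baseline to be the ones scored later, although the endpoint is a change from baseline.
- **Loose wording.** The formula averages sub-domains, but the note counts items. An outside vendor applies this rule.

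Because efficacy appears only in listings, a reader who wants to see change compares one child's rows. No model or group mean would dilute a shift caused only by which sub-domains were scored. Such a shift could be taken for gain or decline. The text of the SAP asks for no component count or mark that would reveal it.

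**Working it through.** The SAP states no figure that can be reproduced here. Section 4.5 says no sample size was estimated, and the documents give no variance or missingness for the VABS-II.

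**What the rule permits**

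The number of sets of two or more out of nine is the sum of C(9,k) for k = 2 to 9, which is 502. Of these, C(9,2) = 36 are pairs. For a given pair, C(7,2) = 21 of the 36 pairs (58%) share no sub-domain with it. The rule therefore does allow different components at different visits.

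**How far the DQ can move**

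Assumed, because the documents are silent: age 48 months, sub-domains missing at random, and a within-child SD of sub-domain age equivalents of 6 months (range 4 to 8).

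SD of (DQ on k sub-domains minus DQ on nine) = SD × √(1/k − 1/9) × 100/48

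| Sub-domains scored | √(1/k − 1/9) | SD 4 | SD 6 | SD 8 |
|---|---|---|---|---|
| 2 | 0.624 | 5.2 | 7.8 | 10.4 |
| 6 | 0.236 | 2.0 | 2.9 | 3.9 |
| 8 | 0.118 | 1.0 | 1.5 | 2.0 |

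Two visits scored on two non-overlapping pairs differ with SD × √(1/2 + 1/2) × 100/48 = 8.3, 12.5 and 16.7 points for SDs of 4, 6 and 8.

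**A worked profile (assumed)**

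Take age equivalents of 30, 24, 20, 26, 22, 18, 24, 28 and 20 months at age 48 months. The sum is 212, the mean 212/9 = 23.56 and the SD 3.97. The nine-component DQ is 23.56/48 × 100 = 49.1.

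- *Two sub-domains.* The lowest pair (18, 20) gives 19/48 × 100 = 39.6 and the highest (30, 28) gives 29/48 × 100 = 60.4. The shift runs from −9.5 to +11.3.
- *Eight sub-domains.* Dropping the 30 gives 22.75/48 × 100 = 47.4. Dropping the 18 gives 24.25/48 × 100 = 50.5. The shift runs from −1.7 to +1.4.

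**Comparison with the effect of age**

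The DQ divides by age at testing. If two visits are 24 weeks (about 5.5 months) apart, an assumed interval, the same unchanged age equivalents give 23.56/53.5 × 100 = 44.0. That is a fall of about 5 points with all nine sub-domains present at both visits. It is larger than the shift from one missing sub-domain. Recomputing both DQs on a common set would remove the composition effect but not this one.

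**Where the shift could enter a result**

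- Section 5.2 names a change from baseline, but sections 7.1, 7.8.2.2 and 8.1 provide only listings for efficacy, and define no efficacy population. No VABS-II change score is planned.
- With no efficacy summaries or tests, no efficacy estimate can be biased by the rule.
- Section 7.8.2.2 lists age-equivalent, raw and standard scores beside the DQ. For the VABS-II, section 10.2.1 speaks of age equivalents only at sub-domain level. If those are the scores listed, a missing component shows as a blank. The phrase about each domain leaves this uncertain.
- The note follows directly on the sentence that averages the nine sub-domains, so its items can only be those sub-domain age equivalents.

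**The case for a change.** The strongest case for a change is that the rule stands in the SAP's own programming conventions, so it is not something left to the protocol. A careful reader of the listing may also be unable to see that the components changed. A remedy would cost little: one corrected word, a component count, a mark where the set differs from baseline and, for those visits, both DQs recomputed on the shared sub-domains.

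The factual part stands. The minimum is two of nine, no common set is required, and the text promises no count.

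The need for a change does not follow. That remedy would keep the two-component minimum and leave every listed DQ as it is, so it concerns annotation and not the rule. Counts and flags in a listing are ordinary shell content, and the shells are not at hand and may already have them. The paired recomputation would add derived efficacy output to an abbreviated report that confines efficacy to listings. It would also depend on the vendor supplying sub-domain values. The large shifts need a child scored on only two of nine sub-domains, and the documents do not suggest that this happened.

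**Conclusion.** The observation is correct, but it does not call for a change. One child's VABS-II DQs may rest on different sub-domains at different visits, and the note uses a loose word for them. The word is a clerical slip with one sensible reading. The missing annotation is a listing detail that analysts settle in the shells.

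Followed as written, the plan gives the same results and conclusions either way, because it contains no VABS-II change score, efficacy summary or efficacy test, and it disclaims any evaluation of effectiveness.

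With one sub-domain missing, the DQ departs from its nine-component value with an SD of about 1.5 points (1.0 to 2.0). With two of nine scored, the permitted extreme, the SD is 7.8 points (5.2 to 10.4). Both figures assume age 48 months, random missingness and a within-child SD of 6 months (4 to 8). None of these inputs comes from the documents, which also do not say how often sub-domains are missing. The conclusion would need to be revisited if the VABS-II DQ were later summarised as change from baseline or used as evidence of effect.

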1. ABBREVIATIONS AND DEFINITION OF TERMS

| Abbreviation | Definition |
|--------------|--|
| AE | adverse event |
| IDDD | intrathecal drug delivery device |
| MPS | Mucopolysaccharidosis |
| MPS IIIA | Mucopolysaccharidosis IIIA or Sanfilippo syndrome Type A |
| IT | intrathecal |
| rhHNS | recombinant human heparan N-sulfatase |
| SAE | serious adverse event |
| SAP | Statistical Analysis Plan |
| SD | standard deviation |
| SOC | system organ class |

2. RATIONALE FOR THE ADDENDUM

Study SHP-610-201 is a Phase IIb, open label extension of study HGT-SAN-093 evaluating the safety and efficacy of 45 mg HGT-1410 administered either every 2 weeks (Q2W) or every 4 weeks (Q4W) via an intrathecal drug delivery device (IDDD), versus no treatment, in subjects at a relatively early stage of mucopolysaccharidosis Type IIIA (MPS IIIA) disease. The study was designed to provide ongoing treatment with HGT-1410 to patients who received HGT-1410 in Study HGT-SAN-093 and to initiate treatment to patients who received no-treatment in Study HGT-SAN-093. The statistical analysis plan (SAP) for interim analysis dated on 26 May 2017 provided a technical and detailed elaboration of the planned interim analysis based on the data with cut-off date of 28 June 2017 (treatment period) for protocol SHP-610-201 amendment 2.

During the treatment period, if a subject discontinued, or withdrew from the study, or the study was stopped by the sponsor, the IDDD was to be removed. If the investigator determined that the IDDD should not be removed (full or partial device) from the subject based upon a safety assessment, then the subject continued in the study under the safety follow-up period upon completion of their last treatment period visit. The safety follow-up period of study SHP-610-201 will monitor the safety of the device up to an additional 3 years or until the device is removed in the last subject.

As of 7 March 2019, Study SHP-610-201 is considered complete as the sponsor has determined that the safety follow-up period may be ended as no safety concerns have been raised and subjects will continue to be monitored by their physicians. This SAP addendum for the safety follow-up period provides the planned analysis on the safety of the device for the subjects who did not have the IDDD removed (full or partial) at the end of the treatment period, based on protocol SHP-610-201 Amendment 2, dated 25 January 2017.

3. GENERAL DESCRIPTION

If the Investigator determined that the device should not be removed from a subject based upon safety assessments at the end of treatment period, the device could remain in the subject (partial [catheter only] or full [port, catheter, and suture wings]) if the subject was doing clinically well and there were no further known risk factors such as infection (eg, meningitis). The device may be partially or fully removed as medically required and determined by the neurosurgeon at a future date.

Subjects who did not have the IDDD removed (partial or full device) at the end of the treatment period of HGT-SAN-093 continued to be observed during a safety follow-up period with visits at the site every 6 months up to an additional 3 years until the IDDD has been fully explanted.

Determined by the sponsor to end the study, the global LPLV for the safety follow-up period was 7 March 2019 and this was the last visit of the study.

4. SAFETY VARIABLES

4.1 Schedule of Safety Evaluations

The schedule of safety evaluations of device was performed every 6 months (Refer to Appendix 5 of the study protocol [Amendment 2]).

4.2 Safety Endpoints

The safety endpoints for the safety follow-up period were:

- Symptom-directed PE
- Clinical laboratory tests (hematology, serum chemistry, urinalysis and standard CSF safety labs); only if indicated for a device-related AE
- X-ray (to check IDDD placement or for any device-related AEs)
- Concomitant medications, therapies, and procedures; only if indicated for a device-related AE
- Device-related AE monitoring
- Postoperative check of IDDD incision (postoperative evaluation can occur within 1-3 days after IDDD explantation)

5. STATISTICAL ANALYSIS

5.1 General Methodology

All statistical analyses will be performed using SAS® Version 9.3 or later.

Tabular summaries will be presented. Continuous variables will be summarized using descriptive statistics [sample size (N), mean, standard deviation (SD), minimum, median, and maximum]. Categorical variables will be summarized using the number and percentage.

For samples associated with multiple tests performed at the same visit (e.g. lab results), the latest valid result will be selected for analysis.

5.2 Analysis Populations

The safety population in safety follow-up period consists of subjects from HGT-SAN-093 whose IDDD was not removed (full or partial) at the end of the treatment period and agreed to participate in the safety follow-up period.

6. DATA DISPLAYS

6.1 Subject Disposition

The number of subjects who signed the informed consent for the safety follow-up period, are in the safety population for safety follow-up period, completed the safety follow-up period, and withdrawn from the safety follow-up period. Reasons for withdrawal will be provided.

Subject disposition will be presented in a by-subject listing.

6.2 Protocol Deviations

An incident involving noncompliance with the protocol, but one which typically does not have significant effect on the subject's rights, safety, or welfare, or the integrity of the resultant data will be considered a protocol deviation.

Protocol violations will be defined as any major protocol deviation that affects study evaluations during safety follow-up period. Subjects will be examined on a case-by-case basis prior to final database lock to determine whether conditions set forth in the study protocol have been violated.

The protocol deviations will be presented in a listing.

6.3 Demographics and Other Characteristics

Demographic and characteristics at the beginning of safety follow-up period, eg, age (years), gender (male, female), race (American Indian or Alaskan Native, Asian, Black or African American, Native Hawaiian or other Pacific Islander, White, Other), and ethnicity (Hispanic or Latino, Not Hispanic or Latino) will be summarized for the safety population in the safety follow-up period. Age, in years, will be calculated by subtracting the date of birth from the date of informed consent for safety follow-up period plus 1 and dividing by 365.25 and then rounding down to two decimal places.

Demographic information will be presented in a by-subject listing.

6.4 Extent of Exposure

Duration of subjects/devices (weeks) in the safety follow-up period will be summarized.

The duration of the subject/device is calculated by subtracting the date of informed consent for safety follow-up period from the device removal date or end of safety follow-up period (whichever is earlier).

A listing for the duration of the device exposure will be presented by subject.

6.5 Safety Analysis

6.5.1 Adverse Events

Device-related AEs were recorded throughout the safety follow-up period. AEs will be coded using the Medical Dictionary for Regulatory Activities (MedDRA) version 13.1 or higher.

AEs will be summarized descriptively. The summary will include the number and percentage of subjects with any AE, device surgical procedure related AE, device-related AE, any device-related serious AE (SAE), and any AE that lead to discontinuation.

AEs will be summarized by system organ class (SOC) and preferred term. The number and percentage of subjects experiencing an AE will be tabulated. Furthermore, AEs deemed as possibly/probably or definitely related to device surgical procedure, or IDDD will be summarized separately. SAEs and AEs which lead to study discontinuation will be similarly summarized.

By-subject listings will be provided for device-related AEs, device-related AEs resulting in death, SAEs, and AEs leading to discontinuation.

